6.2. Secondary Objectives and Endpoints

Secondary Objectives	Study Endpoints
To determine the effect of TP-0184 on the treatment and the hematologic improvement of anemia in terms of hemoglobin increase, reduction in RBC transfusions and RBC Transfusion-Free \geq 8 weeks	
Response rate based on composite response criteria:
 
Hemoglobin increase \geq 1.5 g/dL maintained for a consecutive period of 8 weeks with no transfusions
 
OR
 
Reduction in units of \geq 4 RBC transfusions / 8 weeks (consecutive) compared with the pretreatment transfusion number in previous 8 weeks
 
OR
 
Patients who are RBC transfusion-free over any consecutive 8-week (56-day) period

To determine the effect of TP-0184 on the treatment and the hematologic improvement of anemia in terms of hemoglobin increase, reduction in RBC transfusions and RBC Transfusion-Free \geq 12 weeks	Response rate based on composite response criteria: Hemoglobin increase \geq 1.5 g/dL maintained for a consecutive period of 12 weeks with no transfusions OR Reduction in units of \geq 4 RBC transfusions / 12 weeks (consecutive) compared with the pretreatment transfusion number in previous 12 weeks OR Patients who are RBC transfusion-free over any consecutive 12-week (84-day) period
To measure time to RBC transfusion-free period	Time from first dose of TP-0184 to the first onset of a transfusion-free period for consecutive 8 weeks
To assess median duration of hemoglobin response	Duration of hemoglobin increase \geq 1.5 g/dL maintained for a consecutive period of $>$ 8 weeks with no transfusions.
To assess median duration of reduction in RBC transfusions (4 units / 8 weeks)	Duration of reduction in units of \geq 4 RBC transfusions / 8 weeks (consecutive)
To assess median duration of RBC-transfusion-free period \geq 8 weeks	Duration of RBC transfusion-free period
To assess progression to AML	Proportion of patients progressing to AML, time to AML progression
To assess overall survival	Time from first dose of TP-0184 to death due to any cause
To establish the PK profile of single agent TP-0184	PK parameters of TP-0184 as single agent: C_{max} , C_{trough} , t_{max} , AUC , and possibly others
Phase 2	
To determine the effect of TP-0184 on the treatment and the hematologic improvement of anemia in terms of hemoglobin increase, reduction in RBC transfusions and RBC Transfusion-Free \geq 12 weeks	Response rate based on composite response criteria: Hemoglobin increase \geq 1.5 g/dL maintained for a consecutive period of 12 weeks with no transfusions OR Reduction in units of \geq 4 RBC transfusions / 12 weeks (consecutive) compared with the pretreatment transfusion number in previous 12 weeks OR

	Patients who are RBC transfusion-free over any consecutive 12-week (84-day) period
To measure time to RBC transfusion- free period	Time from first dose of TP-0184 to the first onset of a transfusion-free period for consecutive 8 weeks
To assess median duration of hemoglobin response	Duration of hemoglobin increase ≥ 1.5 g/dL maintained for a consecutive period of > 8 weeks with no transfusions
To assess median duration of reduction in RBC transfusions (4 units / 8 weeks)	Duration of reduction in units of ≥ 4 RBC transfusions / 8 weeks (consecutive)
To assess median duration of RBC-transfusion-free period ≥ 8 weeks	Duration of RBC transfusion-free period
To assess changes in neutrophil count	Proportion of patients achieving hematologic improvement in neutrophil count (HI-N) over any consecutive 8-week (56-day) period and / or decrease in neutrophil count
To assess changes in platelet count	Proportion of patients achieving hematologic improvement in platelets (HI-P) over any consecutive 8-week (56-day) period and / or decrease in platelet count
To assess the safety and tolerability of TP-0184	Assessment of TEAEs; type, frequency, and severity of AEs, and relationship of AEs to TP-0184, TP-0184 dose interruptions and dose reductions
To determine the cardiac safety of TP-0184 administered as single agent	Assessment of the presence of symptoms of CHF (based on NYHA criteria, 12-Lead ECG abnormalities, quantification of cardiac iron by MRI, ECHO, or MUGA scans, and peripheral blood cardiac markers
To characterize steady-state trough PK	TP-0184 plasma trough concentration data at various timepoints. Specifically, pre-dose (trough) samples on Cycle 1 Day 1 of Week 4 and Cycle 2 Day 1 of each Week 5, 6, 7, and 9
To assess progression to AML	Proportion of patients progressing to AML, time to AML progression
To assess overall survival	Time from first dose of TP-0184 to death due to any cause
To assess change from baseline in the Brief Fatigue Inventory (BFI)	The BFI that measures the severity of fatigue based on the worst fatigue experienced during the past 24 hours

Hematopoietic stem cell transplant (HSCT)	To document the percentage and outcome of patients who have achieved a hematologic response and a hematopoietic stem cell transplant (HSCT) during or following treatment with TP-0184
---	--

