6. STUDY OBJECTIVES AND ENDPOINTS

6.1. Primary Objectives and Endpoints

Primary Objectives	Study Endpoints
Phase 1	

 • To assess the safety and tolerability of TP-0184 • To determine the maximum tolerated dose (MTD) or maximum administered dose (MAD) and recommended dose for the future expansion arms of TP-0184 in the Phase 2 part of the study 	Assessment of dose limiting toxicities (DLTs), treatment-emergent adverse events (TEAEs); type, frequency and severity of AEs and relationship of AEs to TP-0184, TP-0184 dose interruptions and dose reductions
Phase 2	
To determine the effect of TP-0184 on the treatment and the hematologic improvement of anemia in terms of hemoglobin increase, reduction in RBC transfusions and Transfusion-Free \geq 8 weeks	
Response rate based on composite response criteria:
 
Hemoglobin increase \geq 1.5 g/dL maintained for a consecutive period of 8 weeks with no transfusions
 
OR
 
Reduction in units of \geq 4 RBC transfusions / 8 weeks (consecutive) compared with the pretreatment transfusion number in previous 8 weeks
 
OR
 
Patients who are RBC transfusion-free over any consecutive 8-week (56-day) period

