13.1.9.1.2. Phase 2 Efficacy Analysis

13.1.9.1.2.1. Response Rate

Response rate is defined as the proportion of patients who achieves response according to the composite endpoint criteria for a consecutive period of 8 weeks ([Appendix 1](#)). Response rate will be estimated with 2-sided 95% exact binomial confidence intervals based on EAS.

13.1.9.1.2.2.12-Week Response Rate

The 12-Week response rate is defined as the proportion of patients who achieves response according to the composite endpoint criteria for a consecutive period of 12 weeks ([Appendix 1](#)). The 12-Week response rate will be estimated with 2-sided 95% exact binomial confidence intervals based on the EAS.

13.1.9.1.2.3. Time to RBC transfusion-free analysis

Time to RBC transfusion-free period is defined as the time from the date of initial dosing at RP2D to first documentation of a transfusion-free period for patients who have one or more transfusion-free periods. Transfusion-free period is defined as the period that a patient becomes transfusion-free for consecutive 8 weeks or longer after treatment of TP-0184. Kaplan-Meier (K-M) survival curve and K-M median (estimate), along with 2-sided 95% CIs, will be provided.

13.1.9.1.2.4. Duration of Hemoglobin Response

Duration of hemoglobin response is defined as the time from the date of first documentation of a hemoglobin response to the date of first documentation of progression of hemoglobin response for hematologic responders. Hemoglobin response is defined as an increase ≥ 1.5 g/dL maintained for a consecutive period of > 8 weeks with no transfusions; hemoglobin progression is defined as a change from baseline < 1.5 g/dL of the hemoglobin or the start of one or more transfusions.

The K-M survival curve and K-M median (estimate), along with 2-sided 95% CIs will be provided.

13.1.9.1.2.5. Duration of Reduction in RBC Transfusion for 8 Weeks Analysis

High transfusion burden patient with reduction in RBC transfusion for 8 weeks is defined as high transfusion burden patients (baseline ≥ 4 U transfusions) patients with change from baseline of equal or more than 4 units transfusions in consecutive 8 weeks in EAS.

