Survival	Endpoints: 
- Overall: death from any cause- Event free: failure or death from any cause- PFS: disease progression or death from MDS- DFS: time to relapse- Cause-specific death: death related to MDS

KEY: CR = complete remission; FAB = French-American-British; Hgb = hemoglobin; HI = hematologic improvement; IWG = International Working Group; MDS = myelodysplastic syndromes; PR = partial remission; PFS= progression-free survival; DFS= disease-free survival.

^a Dysplastic changes should consider the normal range of dysplastic changes (modification).

^b Modification to IWG (2000) response criteria.

Hematologic Improvement According to IWG Criteria (Cheson, 2006)	
Hematologic Improvement ^a	Response criteria (responses must last at least 8 week) ^b
Erythroid Response (HI-E) (pre-treatment, <11 g/dL)	
 - Hemoglobin increase by ≥ 1.5 g/dL - Relevant Reduction in units of RBC transfusions by an absolute number of at least 4 RBC transfusions/8 wk compared with the pretreatment transfusion number in the previous 8 wk
Platelet Response (HI-P) (pre-treatment, <100 X 10 ⁹ /L)	
 - Absolute increase of $\geq 30 \times 10^9$/L for subjects starting with $> 20 \times 10^9$/L platelets - Increase from $< 20 \times 10^9$/L to $> 20 \times 10^9$/L and by at least 100%^b
Neutrophil Response (HI-N) (pre-treatment, <1.0 X 10 ⁹ /L)	
 - At least 100% increase and an absolute increase $> 0.5 \times 10^9$/L^b
Progression or Relapse After HIC	
At least 1 of the following:
 
 - At least 50% decrease from maximum response levels in granulocytes or platelets - Reduction in Hgb by ≥ 1.5 g/dL - Transfusion dependence

KEY: HI-E = hematologic improvement erythroid response; HI-N = hematologic improvement neutrophil response; HI-P = hematologic improvement platelet response; IWG = International Working Group; RBC = red blood cell.

^a Pretreatment counts averages of at least 2 measurements (not influenced by transfusions, ie, no RBC transfusions for 2 weeks and no platelet transfusions for 1 week) ≥ 1 week apart (modification).

^b Modification to IWG (2000) response criteria.

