
To determine the effect of TP-0184 on the treatment and the hematologic improvement of anemia in terms of hemoglobin increase, reduction in RBC transfusions and RBC Transfusion-Free \geq 8 weeks
 
 • (TP-0184-102 Protocol Appendix 1: Consideration of Response for Composite Endpoint) 	
Response rate based on composite response criteria: Hemoglobin increase \geq 1.5 g/dL maintained for a consecutive period of 8 weeks with no transfusions OR Reduction in units of \geq 4 RBC transfusions / 8 weeks (consecutive) compared with the pretreatment transfusion number in previous 8 weeks OR Patients who are RBC transfusion-free over any consecutive 8-week (56-day) period

Secondary

Objectives	Endpoints

To determine the effect of TP-0184 on the treatment and the hematologic improvement of anemia in terms of hemoglobin increase, reduction in RBC transfusions and RBC Transfusion-Free \geq 12 weeks.
 
 • (TP-0184-102 Protocol Appendix 1: Consideration of Response for Composite Endpoint) 	
Response rate based on composite response criteria: Hemoglobin increase \geq 1.5 g/dL maintained for a consecutive period of 12 weeks with no transfusions OR Reduction in units of \geq 4 RBC transfusions / 12 weeks (consecutive) compared with the pretreatment transfusion number in previous 12 weeks OR Patients who are RBC transfusion-free over any consecutive 12-week (84-day) period

Time to RBC transfusion- free period	Time from first dose of TP-0184 to the first onset of a transfusion-free period for consecutive 8 weeks
Median duration of hemoglobin response	Duration of hemoglobin increase \geq 1.5 g/dL maintained for a consecutive period of $>$ 8 weeks with no transfusions
Median duration of reduction in RBC transfusions (4 units / 8 weeks)	Duration of reduction in units of \geq 4 RBC transfusions / 8 weeks. (consecutive)
Median duration of RBC-transfusion-free period \geq 8 weeks	Duration of RBC transfusion-free period

Objectives	Endpoints
Changes in neutrophils	Proportion of patients achieving HI-N over any consecutive 8-week (56-day) period and / or decrease in neutrophil levels
Changes in platelet counts	Proportion of patients achieving hematologic improvement in platelets (HI-P) over any consecutive 8-week (56-day) period and / or decrease in platelet levels

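### Hemoglobin response means 8 weeks in the primary composite but more than 8 weeks in the duration endpoint, so a 56-day responder can drop out of the duration analysis and the median can be biased upward

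*Protocol*

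**What the plan says.** In the primary composite (Protocol 6.1, Phase 2), the hemoglobin limb is a rise of at least 1.5 g/dL "maintained for a consecutive period of 8 weeks with no transfusions". Protocol 13.1.9.1.2.1 also defines the response rate over 8 consecutive weeks, and Appendix 1 lists the hemoglobin criterion per 8 weeks.

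The duration endpoint differs. Protocol 6.2 describes the response as "maintained for a consecutive period of > 8 weeks with no transfusions", for Phase 1 and Phase 2 alike. The synopsis and SAP 1.2 use the same strict inequality. Protocol 13.1.9.1.2.4 turns it into the operational rule: "Hemoglobin response is defined as an increase ≥ 1.5 g/dL maintained for a consecutive period of > 8 weeks with no transfusions". Duration is then measured as "time from the date of first documentation of a hemoglobin response to the date of first documentation of progression of hemoglobin response for hematologic responders", and loss of response is defined thus: "hemoglobin progression is defined as a change from baseline < 1.5 g/dL of the hemoglobin or the start of one or more transfusions".

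Two neighboring definitions are inclusive. Appendix 6, on hematologic improvement, has "Response criteria (responses must last at least 8 week". Protocol 13.1.9.1.2.6, on transfusion-free duration, accepts a period of 8 weeks or longer.

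**The concern.** Protocol 13.1.9.1.2 holds two thresholds for one response and gives no reason. A programmer who codes the written symbol gives two answers for the same patient: a hemoglobin response for the composite, and none for the duration analysis. The patients who fall between the two rules have the shortest responses that count, so the exclusion is not neutral.

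The boundary can also be reached by design. Cycles last 28 days, so qualifying values from Cycle 2 Day 1 to Cycle 4 Day 1 span 2 × 28 = 56 days nominally. At stake are the median duration of hemoglobin response and the clarity of the set it describes. Protocol 13.1.9.1.2.4 adds to the doubt by taking duration in hematologic responders without saying which threshold selects them.

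**Working it through.** The documents give no expected duration, no event count and no number of responders at exactly 8 weeks, so there is no figure to reproduce. The direction follows from the definitions; the size needs assumptions.

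**Direction.** If the strict rule removes a share f of responders, all with the shortest durations, the median of those left is the (1 + f)/2 quantile of the full set (ignoring censoring). For f = 0 this is 0.50; for f = 0.10 it is 0.55. The median therefore rises or stays where it is.

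**Size, reading A: run length from first to last qualifying value, on a visit grid.** Assumptions:
- Time beyond week 8 is exponential with median m weeks, and there is no censoring.
- Readings are g weeks apart.

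The share read as exactly 8 weeks is 1 − 0.5^(g/m). When m is a multiple of g, half of all responders have been lost after m/g readings. The median last qualifying reading is then 8 + m − g weeks under the inclusive rule. Dropping those lost at the first reading after week 8 moves it up one interval, to 8 + m. With g = 2:

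| m (weeks) | Share dropped | Median, at least 8 weeks | Median, more than 8 weeks |
|---|---|---|---|
| 8 | 1 − 0.5^(2/8) = 0.159 | 14 | 16 |
| 16 | 1 − 0.5^(2/16) = 0.083 | 22 | 24 |
| 24 | 1 − 0.5^(2/24) = 0.056 | 30 | 32 |

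The shift is always one interval, here 2 weeks. At m = 16, a 1-week grid gives a share of 4.2% and a shift from 23 to 24 weeks; a 4-week grid gives 15.9% and a shift from 20 to 24 weeks.

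For scale, a 20% response rate in 60 patients is 12 responders. If all 12 responded through hemoglobin, the 2-week grid would drop 12 × 0.056 = 0.7 to 12 × 0.159 = 1.9 patients.

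**Size, reading B: run length read to the day.** Here g = 1/7 week. For m from 4 to 52 weeks the share at exactly 8 weeks runs from 2.4% down to 0.2%, and the shift is 1/7 = 0.14 week (at m = 16, from 23.86 to 24.00 weeks).

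**Size, reading C: run length to documented progression, the end date in 13.1.9.1.2.4.** Take a patient who still qualifies at day 56 and fails at the next visit, about 14 days later. Progression is dated near day 70, so the run exceeds 56 days and the patient stays in. If the week-8 value must itself qualify, only an event dated exactly day 56, such as a transfusion that day, is caught by the strict sign. Section 12.1.5 records transfusions by date, so this would be a rare tie.

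**The case against.** The strongest objection is that the protocol's own end date is first documented progression. On that reading the patients making up the 6% to 16% are not dropped at all. This stands: those shares belong to reading A, which the documents neither state nor rule out.

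The visit grid is also uncertain. The headings of Table 6 show Day 8 and Day 15 visits early on and Day 15 visits later, several with windows of 1 or 2 days, and Table 5 adds weekly hemoglobin checks tied to some dose delays. The hematology row cannot be aligned to its columns in the text available. Windows scatter actual run lengths around 56 days, which weakens the tie without removing it.

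The strict sign may be loose wording for at least 8 weeks, in which case nobody is excluded. That is plausible given Appendix 6 and 13.1.9.1.2.6, but it argues for correcting the text rather than leaving it.

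A reader might go further and infer three things that the documents do not support:
- **That the median duration is too long.** No duration or count at the boundary is given; the shift is upward or zero. A median in patients with more than 8 weeks of response also describes that group correctly. It is biased only as a description of all the composite's hemoglobin responders.
- **That responder counts will disagree between tables.** Section 13.1.9.1.2.1 plans a single composite rate. Reporting by type of response appears only as a recommendation in the notes to Appendix 6.
- **That the primary result is affected.** The composite uses 8 weeks throughout, and a patient with 8 weeks of hemoglobin rise and no transfusions also meets its separate transfusion-free limb.

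**Conclusion.** The inconsistency is real and recurs in the synopsis, Protocol 6.2, Protocol 13.1.9.1.2.4 and SAP 1.2. Coded literally, it can leave 56-day responders out of the duration analysis and bias the Kaplan-Meier median upward. The effect is about one visit interval on reading A, and about 0.14 week or less on readings B and C. All sizes rest on an assumed exponential residual duration without censoring.

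Severity is minor. The endpoint is secondary, and the primary response rate and Bayesian monitoring rules are untouched. SAP Section 2 reports that the study was terminated after two patients and plans by-patient listings only, so no median duration is planned for reporting. The value of the correction lies in a consistent definition, chiefly if these endpoints are reused.

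**What to change.** Replace the strict inequality by at least 8 weeks (56 days) in the synopsis, Protocol 6.2 (both phases), Protocol 13.1.9.1.2.4 and SAP 1.2. State in 13.1.9.1.2.4 that the composite's hemoglobin responders are the set for the duration analysis.

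The same edit should say how run length is read (to the last qualifying value or to documented progression). It should also say whether the duration clock starts at the first qualifying value or when the 8 weeks are complete. That second choice can move a duration by up to 8 weeks, more than the boundary sign does on any grid considered here.

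The cost is wording only. Any median estimated under the inclusive rule would be the same or slightly shorter.

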6.3. Exploratory Objectives and Endpoints

Exploratory Objectives	Endpoints
Phase 1	
To determine pharmacodynamic effects of TP-0184 therapy	Determination of in vivo markers of ALK-2 /ALK-5 inhibition. Markers included, but not limited to: 
 • SMAD/phospho-SMAD signaling • Markers of iron metabolism, including Hepcidin iron panel (serum iron, ferritin, transferrin, soluble transferrin receptor [STR], and total iron binding capacity [TIBC]) • Cytokines TGFβ, IL-6, CRP, EPO
To determine the cardiac safety of TP-0184	Assessment of the presence of symptoms of congestive heart failure (CHF) (based on New York Heart Association [NYHA] criteria), 12-Lead ECGs abnormalities, intensive ECG recordings taken at time of PK draws, assessment of iron accumulation by cardiac magnetic resonance imaging (MRI), ECHO or MUGA scans, and peripheral blood cardiac markers
To determine whether TP-0184 treatment modulates organ iron deposition	Evaluation of cardiac and hepatic iron content by MRI at baseline and during treatment with TP-0184
Metabolites of TP-0184 in patients via Phase 1 data	Profile of potential metabolites of TP-0184 in patients in Phase 1
To assess changes in neutrophil counts	Proportion of patients achieving hematologic improvement in neutrophil count (HI-N) over any consecutive 8-week (56-day) period and / or decrease in neutrophil levels
To assess changes in platelet count	Proportion of patients achieving hematologic improvement in platelets (HI-P) over any consecutive 8-week (56-day) period and / or decrease in platelet count
To assess change from baseline in the BFI	The BFI that measures the severity of fatigue based on the worst fatigue experienced during the past 24 hours

[figure not shown]
Phase 2	
To determine the pharmacodynamic effects of TP-0184 therapy	Determination of in vivo markers of ALK-2 /ALK-5 inhibition Markers included, but not limited to: 
• SMAD/phospho-SMAD signaling• Markers of iron metabolism, including Hepcidin iron panel (serum iron, ferritin, transferrin, STR, and TIBC)• Cytokines TGFβ, IL-6, CRP, EPO
To determine whether TP-0184 treatment modulates iron accumulation and removal in the heart and liver	Evaluation of cardiac and hepatic iron content by MRI at baseline and during treatment with TP-0184

7. INVESTIGATIONAL PLAN

7.1. Overall Study Design

This is a Phase 1/2, open-label clinical study to evaluate preliminary safety and efficacy of TP-0184 to treat anemia when administered to adult patients with IPSS-R low or intermediate risk MDS. The recommended Phase 2 dose (RP2D) will be determined by the maximum tolerated dose (MTD) or maximum administered dose (MAD) in the Phase 1 portion of the study. The study structure is summarized in [Figure 1](#).

Figure 1: Phase 1 and 2 Study Design in Patients with IPSS-R Low or Intermediate Risk MDS

7.1.1. Phase 1 – Dose Escalation

Multiple dose levels of TP-0184, with approximately 1 to 6 patients at each level will be evaluated. There must be at least 3 DLT evaluable patients at a specific dose level if there is a DLT observed in that level. The first dose cohort will start at 20 mg/day every day. Patients will receive their first dose of TP-0184 starting on Cycle 1 Day 1. Dose escalation is planned to proceed with patients receiving each provisional dose level of 40 mg, 60 mg, 90 mg, 120 mg, 160 mg, 210 mg, and 270 mg. Additional dose increments of up to 25% from one dose cohort to the next may occur. In order to determine the recommended Phase 2 dose, dose escalation may continue until one of the following occurs:

1. An MTD is determined.
2. An MAD is determined based on the totality of safety data and medical considerations by the SRC and sponsor.

